Appendix A Figure 1 – Procalcitonin-Guided Algorithm

Appendix B References

## 1.0 Background

The timely use of effective antibiotics can markedly reduce the morbidity and mortality associated with bacterial infections, particularly in the intensive care unit (ICU). However, in this setting, much antibiotic use is empiric, and administered to patients with non-bacterial or non-infectious causes of inflammation that do not respond to antibiotics. This widespread empiric use of antibiotics drives the emergence of multi-drug resistant organisms and antibiotic-associated adverse events, such as *C. difficile* infections. Deescalation of broad-spectrum empiric antibiotic use, slow the development of antibiotic resistance, and reduce complications associated with antibiotic therapy. Thus, antibiotic de-escalation is an important goal of antimicrobial stewardship programs. Specific tests and pathways to predict which patients have bacterial infections and those that would benefit from antibiotic therapy would accelerate de-escalation and greatly facilitate antimicrobial stewardship efforts.

Procalcitonin (PCT) has been investigated as a biomarker for critically ill adult patients with bacterial infection, particularly pneumonia and sepsis. Following bacteria-induced activation of monocytes and adherence of monocytes to endothelial surfaces, procalcitonin is expressed and secreted. PCT levels have been shown to rise rapidly and remain elevated during ongoing bacterial infections, and PCT levels are more specific for bacterial infections than CRP or total white blood cell count. PCT rises approximately 4 hours after bacterial exposure, peaks between 12-24 hours, and has a half-life of 24 hours once the infectious stimulus is removed.

# 2.0 Rationale and Specific Aims

In many adult trials investigating PCT-guided algorithms for antibiotic cessation (refer to section 3.0), a high proportion of providers (up to 50%) chose not to follow algorithm guidance for subjects randomized to the PCT-guided group. Thus, although PCT appears to be a useful guide for safe antibiotic de-escalation in the ICU, the ideal method for implementing the test and integrating it into clinical care in order to maximize its impact in the pediatric population is unclear. Notably, none of the prior trials evaluated PCT-associated outcomes in critically ill children nor integrated PCT testing into antimicrobial stewardship activities.

PCT will be available for routine clinical care across all hospitals at VUMC in July 2017. To better understand the role of PCT in patient management, we will complete a pilot study prior to routine use of PCT in clinical care in the pediatric ICU. We propose the evaluation of a PCT testing and treatment algorithm on patient outcomes in the pediatric ICU, a setting in which PCT-guided antibiotic de-escalation has not been previously studied.

The proposed project will evaluate whether a procalcitonin (PCT) testing and treatment algorithm, implemented through daily antimicrobial stewardship audit and feedback, can promote early and safe antibiotic de-escalation in the pediatric ICU. We will conduct a pragmatic, prospective randomized controlled trial comparing antimicrobial use and outcomes among children admitted to the ICU who receive either: 1) Routine laboratory testing and treatment with antimicrobial stewardship review (control), or 2) PCT testing and treatment with antimicrobial stewardship review (intervention). In both arms, baseline daily review of antimicrobial management by the stewardship team will occur. In the intervention arm, the stewardship provider ([name]) also will recommend PCT testing and antibiotic modifications using a PCT-based treatment algorithm (Fig 1). *This research is not to determine if PCT is a good test; this has already been established and evaluated as part of the FDA approval process. This pragmatic outcomes trial is evaluating if use of the PCT, implemented together with antimicrobial stewardship program oversight, improves the quality of care we can provide for children at VCH.* We hypothesize that patients in the intervention arm will have shorter duration of antibiotic therapy and similar outcomes, as compared to patients in the control arm.

# **Specific Aims**

- 1. Compare antimicrobial utilization among children in the ICU who receive standard-of-care testing plus stewardship vs. PCT-based treatment plus stewardship. We will compare days of antibiotic therapy in the first 14 days following randomization between the study arms. We will test the hypothesis that duration of antibiotic therapy will be 2 days shorter in the group with PCT-guided management vs. the group with standard of care testing and treatment.
- 2. Compare clinical outcomes and safety among children in the ICU who receive standard-of-care testing plus stewardship vs. PCTbased treatment plus stewardship. We will compare mortality, length of stay, recurrence of infection, and antibiotic-associated adverse events (rash, myelosuppression, renal impairment, hepatotoxicity, *C. difficile* infection) between the study arms. We will test the hypothesis that outcomes and safety will be comparable between the study arms.

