# **10.0 Statistical Considerations**

Based on data from studies evaluating PCT use among adult ICU patients, we estimate that median consumption of antibiotics will be 2.0 days less in the PCT group as compared to the control group. Assuming normal distribution, and a standard deviation of 6 days, a sample size of 125 patients per arm will provide at least 80% power to detect a difference in antibiotic duration of at least 2.0 days between study arms. These calculations are based on a chi-squared test with a two-sided Type 1 error rate of 0.05. Per clinical pharmacy data, the average duration of an antibiotic course per patient in VCH ICUs is 4 days, thus a difference of 2.0 days would be clinically significant.

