Exploratory objectives will be to evaluate the impact of a procalcitonin-guided antibiotic algorithm with antimicrobial stewardship guidance on adherence to the procalcitonin-guided algorithm, impact of procalcitonin-guided algorithm on antibiotic stewardship recommendations, impact on antibiotic use in a subgroups of patients with a diagnosis of pneumonia, patients who have antibiotics initiated due to concern for sepsis, patients with initial procalcitonin levels <0.5 ng/mL versus those with initial procalcitonin levels >0.5 ng/mL, patients without comorbidities, and patients admitted to the pediatric intensive care unit vs. those admitted to the pediatric cardiac intensive care unit.

DEFINITIONS

1. Antibiotic escalation: Changing to a broader spectrum antibiotic, addition of one or more antibiotics, or conversion of oral (PO) to intravenous (IV) route.

- 2. Antibiotic de-escalation: Changing to a narrower spectrum antibiotic, cessation of one or more antibiotics, or changing from an IV to PO route of appropriate drug.
- **3. Broad-spectrum antibiotic:** Vancomycin, daptomycin, amikacin, ceftazidime, cefepime, piperacillin/tazobactam, aztreonam, carbapenems
- **4. Antibiotic-associated complications**: Defined as rash, neutropenia, thrombocytopenia, acute kidney injury [defined as increase in serum creatinine >0.3 mg per dL or >1.5-fold from baseline, or urine output <0.5 mL per kg per hour for more than six hours], hepatotoxicity [defined as >2-fold increase in alanine aminotransferase, ALT, or conjugated bilirubin], or *C. difficile* infection
- **5. Multi-drug resistant organism:** Methicillin-resistant *S. aureus*, vancomycin-resistant *Enterococcus*, 3rd generation cephalosporin non-susceptible *Enterobacteriaceae*, multi-drug resistant *Pseudomonas aeruginosa* [resistant to aminoglycosides, cephalosporins, fluroquinolones, and carbapenems), carbapenem-resistant *Acinetobacter* and *Candida* spp. obtained from otherwise sterile sites [i.e. blood or urine cultures]

OUTCOME MEASURES

Primary Outcome Measures

1. Median days of therapy (DOT) per patient of antibiotic therapy (in days) within 14-days post randomization.

Secondary Outcome Measures

- 1. Median DOT per patient of broad-spectrum antibiotic therapy (in days) within 14-days post randomization.

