1.2 Study Population Characteristics

Table: Demographics

- a. Current age on day of study entry (in years): Continuous
- b. Sex at birth: By category (male/female)
- c. Self-reported race, ethnicity and race/ethnicity as defined by NIH reporting standards: By category

2. Health Characteristics/Status at Entry

- a. In pediatric ICU or pediatric cardiac ICU at randomization
- b. Requirement for intravenous vasopressor agents (categorical, yes or no)
- c. Mechanical ventilation (categorical, yes or no)
- Fever (temperature >38.0 deg F) or hypothermia (temperature <35.0 deg F) (categorical, yes or no)
- e. Surgical procedure within 2 weeks prior to enrollment (categorical, yes or no)
- f. Presence of comorbidity
 - Heart disease
 - Gastrointestinal disease
 - Neurologic disease
 - Bone/joint infection
 - Renal disease
 - Hematologic disease
 - Oncologic disease
 - Pulmonary disease
 - Other
 - No comorbidities
- g. Indication for antibiotics
 - Concern for sepsis
 - Pneumonia
 - Meningitis/encephalitis
 - Urinary tract infection
 - Other
- h. Attending physician on the day of enrollment

• Choose 1 of 20 pediatric ICU attending physicians who wrote the progress note for the patient on the day of enrollment

3. Antibiotic Use

Table: Days of antibiotic therapy per patient within 14 days (PRIMARY OUTCOME). Patients who are continued on antibiotics longer than 14 days will be assigned a time of 14 days per antibiotic.

Table: Days of broad-spectrum antibiotic therapy per patient within 14 days. Patients who are continued on broad-spectrum antibiotics longer than 14 days will be assigned a time of 14 days per antibiotic.

Table: Count (%) of patients on any antibiotic longer than 72 hours

Table: Count (%) of patients on broad-spectrum antibiotics longer than 72 hours

Table: Count (%) of patients on IV antibiotics longer than 72 hours

Table: Count (%) of patients on 2 or more antibiotics at 24, 48, 72, and 96 hours after enrollment

Table: Days of IV antibiotic therapy per patient within 14 days. Patients who are continued on IV antibiotics longer than 14 days will be assigned a time of 14 days per antibiotic.

Figure: Time to first antibiotic modification, using the empirical cumulative distribution function.

Figure: Percent of patients on antibiotics within 14 days of enrollment, using a Cox proportional hazards model

4. Sensitivity and Additional Analyses of the Primary Endpoint

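### The hypothesis and power statement are worded as length of an antibiotic course, but the SAP's primary outcome implies drug-days, so a DOT difference would not by itself show a course 2 days shorter

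*Protocol*

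**What the plan says.** **Protocol, Section 2.0, Specific Aims.** Aim 1 states the hypothesis that "duration of antibiotic therapy will be 2 days shorter in the group with PCT-guided management".

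**Protocol, Section 10.0.** The power paragraph opens with consumption: "we estimate that median consumption of antibiotics will be 2.0 days less in the PCT group". It then states the assumptions, "Assuming normal distribution, and a standard deviation of 6 days, a sample size of 125 patients per arm will provide at least 80% power", and the power is said to be enough "to detect a difference in antibiotic duration of at least 2.0 days between study arms", at a two-sided 0.05 level. The 2-day difference is called clinically significant because "the average duration of an antibiotic course per patient in VCH ICUs is 4 days". The trial effects in Section 3.0 are also lengths of treatment: 7 versus 5 days in an adult ICU trial and 6.3 versus 4.5 days in a paediatric pneumonia trial.

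**Protocol, Section 6.0, Study Outcomes.** The primary outcome is a count of treatment days in the 14 days after randomization. It does not say whether a day on two drugs counts once or twice.

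**SAP, Primary Outcome Measures.** The outcome is "Median days of therapy (DOT) per patient of antibiotic therapy (in days) within 14-days post randomization".

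**SAP, 3. Antibiotic Use.** For the primary-outcome table, patients who continue past day 14 are "assigned a time of 14 days per antibiotic".

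**The concern.** The primary outcome should be the quantity that the hypothesis names and that the trial was powered on. Here the hypothesis, the clinically relevant difference and the powered difference are worded as how long a course lasts, while the SAP's counting rule points to drug-days summed over drugs. These are the same number only for a child who never has two antibiotics on one day.

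Two things are at stake. First, a significant fall in DOT could be reported as treatment 2 days shorter when part or all of it came from fewer concurrent drugs. Second, the difference and SD behind the power statement are not given for the endpoint as the SAP counts it, so the reader does not know what power the primary test has. Because neither document defines the counting unit, two analysts could also compute different primary endpoints from the same records and each defend the choice.

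**Working it through.** **1. The plan's own power figure.** Inputs from Protocol Section 10.0: n = 125 per arm, difference d = 2.0, SD s = 6, two-sided 0.05.

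- Standard error = s × √(2/n) = 6 × √(2/125) = 0.759.
- Power = Φ(d/SE − 1.96) = Φ(2/0.759 − 1.96) = Φ(0.675) = 75.0%. A t-test gives 74.7%.
- n for 80% power = 2 × (1.96 + 0.842)² × 36/4 = 141.3, so 142 per arm.
- With the Wilcoxon efficiency of 0.955 under normality, power is about 73% and about 149 per arm are needed.
- The SAP's 280 participants, if split equally, make 140 per arm: 79.6%.
- A one-sided 0.05 test needs 112 per arm, so 125 would reach 80%, but the protocol states two-sided.
- The protocol names a chi-squared test. That cannot be reproduced because no proportions are given.

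The stated 80% does not reproduce. This holds whatever the counting unit is.

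**2. Which unit each document implies.** Aim 1, the detectable difference, the 4-day average and the cited effects all describe the length of a course. A cap of 14 days for each antibiotic makes sense only if days are counted per drug and added: two drugs running past day 14 total 28, which is impossible for calendar days in a 14-day window.

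**3. Whether the two units can differ in this trial.** They can. Section 6.0 of the protocol describes standard care as one or more broad-spectrum agents. The SAP tabulates patients on at least two antibiotics at 24, 48, 72 and 96 hours. Its Definitions count stopping one of several drugs as de-escalation and adding one as escalation. A constructed example:

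| | Calendar days | Drug-days |
|---|---|---|
| Two drugs, 4 days each | 4 | 4 + 4 = 8 |
| One drug stopped after day 2, the other given for 4 days | 4 | 4 + 2 = 6 |
| Difference | 0 | 2 |

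**4. Power on the drug-day scale.** The documents give no mean, SD or expected difference in drug-days, so every value below is an assumption. Same formula, 125 per arm, two-sided 0.05:

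| Difference (drug-days) | SD | Power | n per arm for 80% |
|---|---|---|---|
| 2 | 7.5 | 56% | 221 |
| 2 | 9 | 42% | 318 |
| 3 | 9 | 75% | 142 |
| 4 | 12 | 75% | 142 |
| 3 | 7.5 | 89% | 99 |
| 4 | 9 | 94% | 80 |

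Counting per drug can enlarge the SD and the difference together. If both scale by the same factor, power does not change. The direction is undetermined.

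**5. Whether SD 6 fits calendar days capped at 14.** The largest SD on a 0 to 14 scale with mean m is √(m(14 − m)). At means 4 and 2 it is √40 = 6.32 and √24 = 4.90 (pooled √32 = 5.66), so SD 6 in both arms is impossible. At means 7 and 5 it is 7.0 and √45 = 6.71, so SD 6 is large but possible.

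**The case against.** **The wording is loose on both sides.** The protocol also speaks of utilization, consumption and days of treatment. The SAP never defines DOT as a sum, and its regression paragraph calls the same outcome a duration. Neither document uses the word calendar. A reader might infer that a clearly defined calendar-day endpoint was replaced by another one. The documents do not show that. They show an undefined unit used inconsistently, with the hypothesis leaning one way and the counting rule the other.

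**The SD has no stated source or counting unit.** A reader might infer that SD 6 is a calendar-day figure, or that it is impossible on that scale. Only its sentence ties it to duration. The impossibility in step 5 needs means of 4 and 2, whereas the 2-day effect is taken from trials with longer courses.

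**Power may not be worse.** A reader might infer that moving to DOT costs power. That follows only if the SD grows while the difference stays at 2, and nothing in the documents supports holding it there.

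**DOT suits the trial's purpose.** The trial aims to promote de-escalation. Dropping one of two drugs is de-escalation, and calendar length would miss it. This stands: DOT is a defensible endpoint, and the comparison of DOT between arms is not invalidated. The mismatch lies in the hypothesis and power statement.

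**Time on treatment is partly covered.** The SAP has a Cox model for time to cessation within 4 and 10 days, a figure of the percentage still on antibiotics over 14 days, and use beyond 72 hours. These would help reveal fewer drug-days without earlier cessation. But none is a listed primary or secondary outcome, and none tests a 2-day difference to day 14.

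**It is late to change the sample size.** The SAP is dated June 4, 2019, and the protocol projects an end on June 30, 2019. So restated power would serve honest reporting and would hardly change recruitment.

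**Conclusion.** The point holds in this form. The hypothesis, the clinically relevant difference and the powered difference are worded as length of a course, and the SAP's primary outcome is, by its cap, a drug-day count. A DOT difference of 2 can arise with a calendar difference of 0, so it does not by itself support a claim of treatment 2 days shorter. How far the two measures would part in this population cannot be sized, because the documents do not give the frequency or length of concurrent treatment.

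Power for the SAP's endpoint is unknown and should not be described as lower. The one firm number is separate from the unit: about 75% on the protocol's own inputs, against a claim of at least 80%.

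The conclusion rests on reading the per-antibiotic cap as a sum over drugs. If the sponsor meant calendar days on any antibiotic, that rule is the text to correct. The power figures assume independent patients, equal arms, and normality where the t-test or Wilcoxon efficiency is used.

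**What to change.** - Define the primary outcome identically in protocol and SAP: drug-days or calendar days on any antibiotic, how a day on two drugs counts, and what the 14-day cap applies to.
- If DOT stays primary, restate the Aim 1 hypothesis, the clinically relevant difference and the power in drug-days, with a sourced SD. If no such SD exists, state that power for DOT was not established. In either case, correct the 80% to about 75% on the stated inputs.
- Prespecify calendar days on any antibiotic to day 14 as a secondary outcome, and rest any statement about shorter duration on it alone.

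The cost is wording in both documents and one more derived variable from data already collected. The downside is that the stated power becomes less favourable or is declared undetermined.

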# 3.0 Animal Studies and Previous Human Studies

Multiple studies have demonstrated that PCT-guided algorithms for antibiotic cessation result in significantly shorter antibiotic courses, with no increase in adverse clinical outcomes, in the treatment of pneumonia in adults and children, and in adults with sepsis. Based on these studies, the US FDA has recently expanded PCT indications to include its use to guide antibiotic management in adult patients with respiratory tract infections and/or sepsis. Baer *et al* (*PLoS One*, 2013) demonstrated that antibiotic courses could be safely and significantly shortened for pediatric patients with pneumonia from 6.3 days to 4.5 days under PCT guidance. Levels were measured on presentation and at days 3 and 5 of therapy with strict adherence to PCT level guidelines: discontinuation of antibiotics was encouraged upon clinical stabilization and when PCT values fell below 0.25  $\mu$ g/L or, for patients with initial PCT values > 10  $\mu$ g/L, when levels decreased below 90% of the initial value. In a recently published randomized, controlled, multi-center trial of 1575 adult ICU patients, de Jong *et. al* (*Lancet Infectious Diseases,* 2016) demonstrated that PCT-guided antibiotic treatment, with antibiotic de-escalation when PCT level fell to 80% of its peak value or to 0.5  $\mu$ g/L or lower, could safely and significantly shorten antibiotic

duration from 7 days in the standard of care group to only 5 days in the PCT-guided group, without a significant difference in mortality rates.

### 4.0 Inclusion/Exclusion Criteria

Eligible subjects will be identified on admission to an intensive care setting by monitoring daily ICU census in EPIC.

Subjects will be enrolled if they:

- Are prescribed or administered antibiotics in the hospital within 1 calendar day of enrollment.
- Are admitted to the pediatric ICU (units 5A or 5C)
- Have parents or legal guardians who provide informed consent, or provide consent themselves if 18 years of age or older
- Provide assent if >7 years of age

Subjects will be excluded if they meet any of the following criteria:

- Are not prescribed antibiotics in the hospital
- Receive intravenous antibiotics within 7 days prior to identification for study enrollment
- Primary or secondary immune deficiency
- History of malignancy, bone marrow transplant or solid organ transplant
- A diagnosis of cystic fibrosis
- Neonates < 34 weeks gestation
- Patients receiving treatment for endocarditis, osteomyelitis, meningitis, mediastinitis, or other invasive infection, for which long durations of antibiotics are needed.
- Do not provide informed consent/assent

# 5.0 Enrollment/Randomization

The study will begin after PCT becomes available at VUMC, and after IRB approval. Enrollment will occur over 16 months.. Eligible subjects will be identified on admission to an intensive care setting by monitoring daily ICU census and a clinical pharmacy surveillance platform (Sentri7). Investigators will obtain consent (for all subjects) and assent (for subjects >7 years of age) by discussing the study with the patient and guardian in a private room, using the IRB-approved consent and assent forms. Privacy will be assured, Subjects will be permitted 24 hours to make a decision to participate. Investigators will assure that subjects comprehend the nature of the study by asking questions to assess their understanding of study objectives and procedures, and the risks and benefits of participation. All steps will be taken to avoid coercion. Subjects will be assured that if they decline to participate, they will continue to receive standard of care treatment in the PICU. Investigators will complete a combined consentauthorization document.

Enrolled subjects will receive either: 1) Standard of care testing and treatment with antimicrobial stewardship review (control), or 2) PCT testing and treatment with antimicrobial stewardship review (intervention).

#### 6.0 Study Procedures

#### Study Design

The proposed study is a prospective randomized controlled trial among children admitted to the ICU setting at Vanderbilt Children's Hospital (VCH). Enrolled subjects will receive one of two management strategies: 1) Standard of care with antimicrobial stewardship review (control), or 2) PCT testing and treatment with antimicrobial stewardship review (intervention). All subjects in both arms will have baseline audit of antimicrobial orders with feedback to providers by the antimicrobial stewardship team. For subjects in the intervention arm, the stewardship team will additionally recommend PCT testing and treatment per algorithm (Fig 1). PCT will be used in conjunction with clinical status and exam, and results of radiographic and laboratory studies, to make medical decisions about antibiotic therapy. The PCT will never be used as the sole basis for making decisions to modify or stop antibiotic therapy. The antibiotic stewardship clinicians will review all enrolled subjects (in control and intervention arms) and provide recommendations regarding antimicrobial therapy.

The ultimate decision to obtain PCT testing and/or adhere to the PCT algorithm or stewardship recommendations will be at the discretion of the ICU attending physician. Preliminary discussions with ICU faculty have revealed that they are highly supportive of the proposed study, and would be willing to adhere to the study protocol.

